7.5 Testing at Ascend Clinical Laboratory	20
7.6 Test Results	21
7.7 Data Collection	21
7.8 Data Confidentiality Procedures.....	22
7.8.1 RADx-UP Common Data Elements Survey	22
7.8.2 Limited PHI Electronic health record	22
7.9 Data extraction and transfer procedures	23
7.9.1 RADx-UP Survey	23
7.9.2 Limited PHI Data.....	23
7.10 Statistical Analysis Plan.....	23
8.0 DATA AND SAFETY MONITORING.....	23
9.0 EXIT SURVEY	25
10.0 REFERENCES.....	25
11.0 APPENDIX	30

PROTOCOL OVERVIEW

In this study we plan to offer SARS-CoV-2 screening tests at up to 62 selected US Renal Care dialysis in order to: reduce transmission, and detect early cases and prevent serious illness. This clinical trial is part of the NIH Rapid Acceleration of Diagnostics- Underserved Populations (NIH-RADx-UP) initiative (<https://radx-up.org/about/>), whose goal is to improve access to COVID-19 testing in underserved communities. Patients receiving dialysis have an 8-fold higher risk for hospitalization and 15-fold higher risk for death from COVID-19 compared with the general population. Patients receiving dialysis also disproportionately belong to racial/ethnic minority and economically disadvantaged groups. Thus the goals of this project are to increase availability of highly sensitive and specific testing for SARS-CoV-2 infection in a medically vulnerable and disadvantaged population.

Approach: This is a pragmatic cluster (facility-level) randomized clinical trial to test the patient level acceptability of two strategies for offering test-based screening at the dialysis facility. We will be offering anterior nares, rtPCR tests at a static frequency (arm 1) versus a dynamic frequency anchored to county COVID-19 spread (arm 2). After a pilot in four facilities, we plan to scale up the study to up to 62 dialysis facilities within US Renal Care. Ascend Clinical Laboratory will provide testing supplies, process testing, and return results to facilities. Abbott Molecular will provide supplies for the Alinity m SARS-CoV-2 rtPCR assay (approved under FDA EUA) at discounted costs. Stanford University will lead study design, data analysis, and dissemination of results.

Arm 1—Static frequency: selected facilities will offer testing once every two weeks to all patients coming to dialysis

Arm 2—Dynamic frequency: selected facilities will offer testing to all patients coming to dialysis once a week if county COVID-19 spread is high, once every two weeks if county COVID-19 spread is low or moderate, and once a month if COVID-19 spread is minimal or eliminated.

Intervention time frame: 3 months

We will assess the following outcomes:

- 1 Patient level test acceptability (primary outcome)
- 2 Facility level Deaths
- 3 Facility level Hospitalization

The overall goal is to identify a highly acceptable universal testing strategy for patients receiving dialysis and prevent serious complications from SARS-CoV-2 by identifying cases early.

2.0 BACKGROUND

Patients receiving dialysis are one of the highest risk groups for serious illness with SARS-CoV-2 infection. In addition to the inherent risks of travel to and dialysis within indoor facilities, patients receiving dialysis are more likely to be older, non-white, from disadvantaged backgrounds, and have impaired immune responses to viral infections and vaccinations. Universal testing offered at hemodialysis facilities could shield this vulnerable population from exposure, enable early identification and treatment for those affected, and reduce transmission to other patients and family members.

2.1 Patients receiving dialysis are an underserved, medically vulnerable population

The average patient on dialysis in the US is between 65-74 years old and has advanced diabetes causing kidney failure(1). Among patients on hemodialysis, 47% have diabetes as the primary cause ESKD, 62% have cardiovascular disease, and 32% have heart failure. Patients receiving dialysis are also disproportionately from racial/ethnic minority groups(1, 2). One striking piece of data encapsulates the disproportionate burden of ESKD on minority populations: 12% of persons in the US self-identify as Black; in contrast, 30% of patients on dialysis are Black.

Thirty-five percent of patients on dialysis in the US live in poor neighborhoods (i.e., neighborhoods with 20% of persons living below the federal poverty line)(3). In a seminal analysis, Volkova et al.(4) determined that persons living in poor neighborhoods had 3 to 5-fold higher likelihood of incident ESKD (compared with neighborhoods with < 5% of persons living below the poverty line), with larger risks experienced by Blacks compared with whites.

Requirement for in-center visits to complete dialysis can amplify the risk for SARS-CoV-2 transmission within the facility and in the community(5). Patients wear masks but may need to take them off to ingest prescribed medications and nutritional supplements; they have interactions in lobbies with friends on dialysis, often their only social interaction of the day. As with the rest of the US population, 40% of patients receiving dialysis with SARS-CoV-2 infection may be asymptomatic(6), potentiating the risk for transmission. Corbett et al.(5) report from the UK that dialysis facility characteristics such as distance between dialysis chairs, waiting room size, and staff symptomatic illness all correlated with facility COVID-19 cases. In the context of the COVID-19 pandemic this setup is a worst case scenario: a highly comorbid, elderly and socially disadvantaged population, with impaired immune responses and frailty, sharing small indoor spaces for prolonged periods.(7, 8)

2.2 Patients receiving dialysis face high risk for death & hospitalization from COVID-19

Centers for Medicare & Medicaid Services (CMS) data indicate that patients receiving dialysis have the highest rate of COVID-19 hospitalizations among susceptible groups, 8-fold higher than population average(9). Early on in the pandemic, nearly one third of patients who were hospitalized with COVID-19 in New York(10) died. Despite improvements in treatment, a nationwide analysis continues to estimate mortality rates exceeding 20%(11), and CMS data continue to report high numbers of excess deaths. In addition to the innate factors of older age, comorbidity, and clustering, there has been also “renal-ism” in use of treatments(12, 13). For

example, remdesivir—an early promising therapy—was considered ‘contra-indicated’ in ESKD, although any concerns for a theoretical risk from its carrier had been previously debunked(14, 15).

2.3 Even after vaccination, patients receiving dialysis will contend with prolonged risks due to impaired immune responses

Experts predict recurrent ‘outbreaks’ of COVID-19 extending into 2025 if infection or vaccination does not result in sustained immunity (16-20). Boosters, and requirements thereof for subsets of the population are as-yet uncertain, but it is becoming clear that a sizeable portion of patients on dialysis (21-23), patients on immunosuppression(24), and other subgroups(25) have impaired responses to vaccination. Prior data on vaccination in the dialysis population corroborates emerging data(26, 27). In multiple prospective studies of Hepatitis B, only 60-70% of vaccinated patients receiving dialysis mounted a sufficient response and, of these, 40% lost immunity within 1-3 years(28, 29). In influenza studies, one focused on H1N1 strain alone(30) and one(31) on trivalent vaccine including H1N1 strain, 57% and 46% of patients receiving dialysis mounted sufficient titers to be considered immune to H1N1 at 4 weeks, compared with 90% or more of healthy volunteers. Patients receiving dialysis will likely face excess risk for COVID-19 despite vaccination just as they do for influenza(32) despite universal influenza vaccination protocols in dialysis facilities.

2.4 Universal screening of high-risk clustered populations will simplify screening protocols, prevent transmission, and identify early disease for rapid treatment with monoclonal antibodies.

Current non-standard testing protocols across and within dialysis facilities lead to considerable uncertainty and may miss or delay diagnoses at the cost of patients’ lives. Evidence from other settings suggests that universal screening in a clustered population dramatically improves the detection rate. For example, a universal screening protocol implemented in 11 nursing home facilities led to a 3-fold higher detection of SARS-CoV-2(33) (34, 35). Similar data (of only two secondary transmissions) were reported from a boarding school implementing universal rtPCR testing(36). Thus, universal screening has the potential to save lives in high-risk, clustered populations.

Since dialysis facilities are staffed by ably trained nurses, technicians, dieticians, and social workers, dialysis facilities can also serve as a conduit for the provision of primary health care to patients receiving dialysis *and* for mitigation of risks for SARS-CoV-2. Many foundational primary care interventions, including vaccines, diabetic foot checks, and social support assessments, occur at the dialysis facility, which many patients consider as their ‘medical home.’ Facilities are partnered with central laboratories, with processes in place for rapid specimen shipment and results return in the electronic medical record. Most importantly facilities stock monoclonal antibodies. Data from patients treated with bamlanivimab at US Renal Care suggest dramatic improvements in requirement for hospitalization: hospitalization rate was 15% among 40 patients receiving the antibody, compared with 57% among patients on dialysis with COVID-19 matched for age, sex, self-reported race, and diabetes status(37). The two other large dialysis organizations reported <10% hospitalization rate post bamlanivimab administration(37).

Mina and Anderson present a framework for selecting and applying testing strategies based on the health scenario. Patients on dialysis require testing for both “personal health” (given their high vulnerability) and “public health” (given the risk for transmission) indications(38).

3.0 TRIAL OBJECTIVES

3.1 To identify a highly acceptable SARS-CoV-2 testing strategy in dialysis facilities

The primary objective of this study is to offer SARS-CoV-2 testing to an underserved population. We hypothesize that the community COVID-19 case rate will be associated with test acceptability. We will test this hypothesis by offering testing either at a static (every two weeks) frequency (arm 1) or offering testing at a dynamic frequency tied to community COVID-19 rates. Among the two arms, we will assess differences in:

- 1) Primary outcome (assessed during the three-month period of the intervention): Proportion of offered tests accepted: # of times individuals respond yes / total # of times individuals are asked to perform the test during the 3-month period of the intervention

3.2 To evaluate effectiveness of the SARS-CoV-2 testing strategies in patients receiving dialysis

We will evaluate the clinical effectiveness of the two testing strategies by reporting and comparing:

Secondary outcomes (assessed up to one-month post completion of intervention):

- 2) Hospitalizations
- 3) Deaths

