5.3 Governing Body Review

All dialysis facilities have a CMS mandated governing body responsible for facility-level operations. The governing body typically includes the medical director (nephrologist), facility manager, and members of the nursing or social work teams. This governing body meets monthly to review facility data. Among the selected facilities, we will review study goals and procedures for the selected facilities' governing bodies. The governing body can request to opt out of the study.

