5.7 Dynamic Testing Frequency

Facilities randomized to the dynamic arm will offer dialyzing patients rtPCR testing according to an adaptive testing strategy based on current estimates of community COVID-19 transmission. We anticipate that community transmission and risk of COVID-19 will evolve over the lifetime of this trial. Wastewater SARS-CoV-2 RNA loads can be used to detect COVID-19 incidence rates as low as 1 per 100 000 persons and have been demonstrated to correlate with clinical case data during the COVID-19 pandemic (Wolfe 2021, Karthikeyan 2021, Graham 2021, Huisman 2022). We will combine disease surveillance estimates based on wastewater samples with community surveillance data from the CDC to monitor current epidemic trends at the county level and guide testing strategy assignment in real time.

Using data from the preceding week, we will establish testing frequency for each facility for a period of four weeks. Facilities with high, medium, and low evidence of community COVID-19 transmission will be assigned to once weekly, once every two weeks, and once every four weeks testing respectively. After each four-week intervention period, facilities will be assigned a new testing strategy based on the current county level of COVID-19 transmission.

The data that will inform the facility assignment to testing strategies will be:

- 1) SARS-CoV-2 RNA wastewater percentile levels
Or
- 2) Number of new cases per 100,000 persons
Or
- 3) Number of hospitalizations per 100,000 persons

High, medium and low evidence of community COVID-19 transmission will be determined by pre-defined thresholds in these indicators (Table 1). If indicators suggest different transmission levels, the highest level is selected, with facilities falling into the highest frequency of testing when any one of the indicator criteria are met.

If at any given time during the trial, 95% of facilities do not meet criteria for high frequency testing then facilities will be assigned to testing frequency strategies using trial-wide tertiles of current COVID-19 incidence.

Table 1. Thresholds for levels of community COVID-19 risk by indicator

Community Risk Level	Wastewater	Clinical indicators	
	Viral percentile level ^a	New COVID-19 cases ^b	New COVID-19 hospitalizations ^b
Low	< 20 %	<50	<10
Moderate	20–59 %	50–199	NA
High	≥ 60 %	≥200	≥10

^a SARS-CoV-2 RNA wastewater levels with respect to local historical range

^b Total number per 100 000 persons in the past 7 days

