5.9 Adherence

Stanford University investigators can monitor intervention adherence in a non-obtrusive manner at each dialysis facility, both in terms of the number and frequency of rtPCR tests performed, by regularly reviewing all dialysis visits and rtPCR test data recorded in the electronic health system. Based on this information, Stanford University investigators can generate reports about performance of participating facilities. These reports will be provided to the dialysis provider organization research teams who, in turn, can communicate with clinical leadership at the

dialysis facilities. The Stanford University investigators can additionally generate reports comparing adherence rates between participating dialysis units, which can be reviewed at monthly dialysis unit quality improvement meetings.

COVID-19 surveillance testing, as well as other COVID-19 safety protocols, are part of standard practice at all dialysis units. Accordingly, members of the multi-disciplinary care teams in dialysis units are trained to pay close attention to adherence these protocols. The multi-disciplinary teams will be encouraged to review adherence to rtPCR testing protocols 1) during routine monthly multidisciplinary care rounds, 2) during routine monthly quality improvement meetings, or 3) through direct communication from the trial project managers to the dialysis unit clinical leadership. To encourage adherence at an individual patient-level at units randomized to both static and dynamic testing interventions, informational materials about the trial, the risks of COVID-19 for patients receiving dialysis, and methods to prevent COVID-19 transmission, will be provided. In addition, at dynamic intervention units, current data about county-level COVID-19 community transmission will be provided to both trial participants and clinical staff. Treating nephrologists will be encouraged to discuss the importance of rtPCR testing for SARS-CoV-2 as a method to prevent transmission with trial participants and clinical staff.

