7.3 Randomization

We will sort US Renal Care facility ID numbers by location and facility size. Within US census region (Northeast, Midwest, South, and West) and facility size strata (< median or >=median size), we will randomly select two facilities per county, oversampling by 30%.

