7.10 Statistical Analysis Plan

We will compare the proportion of the total number of times individuals accept performing the test (# of times individuals respond yes / total # of times individuals are asked to perform the test) in the static versus dynamic testing frequency arms. We will use a log-binomial model predicting the probability of acceptability (Y) from intervention arm applying a generalized estimating equation (GEE) approach to take into account the clustering by dialysis facility and the multiple observations per patient. A similar method will be used for estimating the effect of the intervention on the outcome of death or hospitalization. Alternatively, we will use a frailty model which allows for a survival analysis of heterogeneous populations due to the clustering within facilities and multiple observations for each individual(46).

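### Section 3.1 says the arm comparison will test whether community case rate is associated with acceptability, but the only acceptability model (Section 7.10) has arm as its sole predictor, so that hypothesis gets no direct test

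*Combined protocol and SAP*

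**What the plan says.** Under the primary objective, Section 3.1 states: "We hypothesize that the community COVID-19 case rate will be associated with test acceptability". It says this will be tested by offering testing at a static or a dynamic frequency, and names as primary outcome the between-arm difference in the proportion of offers accepted.

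Section 7.10 gives the only model for acceptability: "We will use a log-binomial model predicting the probability of acceptability (Y) from intervention arm", fitted with a "generalized estimating equation (GEE) approach to take into account the clustering by dialysis facility and the multiple observations per patient". Section 5.10 adds only that repeated observations and clustering will be accounted for. In the text available, no section uses case rate or transmission level as a covariate, interaction, subgroup or within-arm analysis.

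Three design features bear on what the arm contrast measures:

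- **Offer frequency.** County indicators set the frequency in the dynamic arm. In Section 5.7, facilities at high, medium and low transmission "will be assigned to once weekly, once every two weeks, and once every four weeks testing respectively". Static facilities offer a test every two weeks throughout.
- **Information.** Section 5.9 says that "at dynamic intervention units, current data about county-level COVID-19 community transmission will be provided to both trial participants and clinical staff". No such data are planned for static units.
- **Sampling.** Section 7.3 says that "we will randomly select two facilities per county, oversampling by 30" percent. Splitting each county pair between arms is implied by Sections 5.2 and 7.3 but not stated.

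**The concern.** The hypothesis concerns an exposure, county case rate, that varies across counties and over time. The planned test concerns a different variable, the arm. If county pairs are split, case rate is likely to be balanced between arms, so arm is not a proxy for it. Case rate reaches the arm contrast mainly because dynamic facilities make more of their offers when transmission is high. Offer frequency itself and the county information can also move the contrast, with no case-rate association at all.

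What is at stake is the reporting of a stated hypothesis. Read literally, Section 3.1 lets a null arm result be reported as evidence against a case-rate association, and a positive one as evidence for it. Neither follows. A case-rate analysis chosen after the data are seen would be a weak substitute.

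**Working it through.** **1. The plan's own sample size (Section 5.5).** Inputs: acceptance 0.40 versus 0.65, alpha 0.05 (two-sided assumed), power 80%, ICC 0.5, 40 patients per facility.

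- Variance inflation: 1 + (40 − 1) × 0.5 = 20.5.
- Unclustered n per arm: (1.96 + 0.842)² × (0.40 × 0.60 + 0.65 × 0.35) / 0.25² = 58.7.
- Clustered: 58.7 × 20.5 = 1,203.5 patients; divided by 40 this is 30.1, so 31 facilities per arm.
- Total: 2 × 31 × 40 = 2,480.

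The stated figure is reproduced. It sizes the arm contrast, not a case-rate association.

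**2. How much of a case-rate association reaches the arm contrast.** From Section 5.7: 4, 2 and 1 offers per four-week block at high, medium and low transmission in the dynamic arm, against 2 throughout in the static arm. My assumptions, which the documents do not give: acceptance of 0.60, 0.40 and 0.20 at the three levels, one third of facility-time at each, the same mix in both arms, no other effect of arm, and simple pooling over offers.

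- Static: (0.60 + 0.40 + 0.20) / 3 = 0.400.
- Dynamic: (4 × 0.60 + 2 × 0.40 + 1 × 0.20) / (4 + 2 + 1) = 3.4 / 7 = 0.486.
- Arm difference: 8.6 points, from a high-versus-low association of 40 points.

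**3. Power for that difference.** With 31 × 40 = 1,240 patients per arm and inflation 20.5:

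- SE = √[20.5 × (0.400 × 0.600 + 0.486 × 0.514) / 1,240] = 0.090.
- Power = Φ(0.086 / 0.090 − 1.96) ≈ 16%.

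Under these assumptions a strong association would usually give a non-significant arm test.

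**4. The opposite direction.** Suppose there is no case-rate association but the county information alone raises acceptance from 0.40 to 0.50 (assumed).

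- SE = √[20.5 × (0.24 + 0.25) / 1,240] = 0.090.
- Power = Φ(0.10 / 0.090 − 1.96) ≈ 20%.

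An effect as large as the planned 25 points would be detected with about 80% power. A false claim of support is therefore possible, but it needs a much larger effect of frequency or information.

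**5. Precision of a direct look within the static arm.** Take high versus low level, fixed over the trial, with 31 / 3 ≈ 10.3 facilities at each level and acceptance of 0.60 and 0.20.

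- SE = √{20.5 × [0.24 / (40 × 10.33) + 0.16 / (40 × 10.33)]} = 0.141.
- 95% half-width: 1.96 × 0.141 ≈ 28 points.

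This counts each patient once and ignores county pairing. If only 2 or 3 facilities fall in one level, the interval is much wider or uninformative. Changes of level within a facility across blocks would add information.

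**The case against.** The strongest reply is that this is mostly wording. Section 3.1 itself puts the hypothesis into operation as a difference between arms. Its title, the Protocol Overview, the sample size, the outcome definition and the model all treat the question as a comparison of strategies, and one sentence is out of step. Much of that stands, and it is why rewording Section 3.1 comes first in the fix. But the section does say that the hypothesis will be tested, under the primary objective, and the planned test does not test it.

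A second reply is that the magnitudes are assumed. That also stands: gradient and level mix are mine, and the 8.6 points is an illustration.

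Two stronger readings are tempting.

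- **That the association would vanish almost entirely from the arm contrast.** With an exchangeable working correlation of 0.5 and each facility held at one level for the whole trial, the difference is only about 0.04 points. But Section 5.7 reassigns frequency every four weeks. If the level is redrawn independently each block, the same working correlation gives a difference of 5.7 percentage points.
- **That the trial is likely to announce false support.** Step 4 shows that a 10-point information effect would reach significance only about one time in five.

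Two neighbouring matters are separate points and carry no weight here. Section 7.10 does not name a working correlation. The Protocol Overview describes the tiers differently from Section 5.7 ("once every two weeks if county COVID-19 spread is low or moderate, and once a month if COVID-19 spread is minimal or eliminated"), and those passages need to be reconciled by the authors.

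**Conclusion.** The mismatch between hypothesis and analysis is real and follows from the text alone, without any assumed number. The arm contrast compares two strategies and is only indirectly sensitive to case rate, so neither a null nor a positive result should be reported as settling the case-rate hypothesis. The main risk is a false null: in the illustration, 40 points become 8.6, with about 16% power. That size depends on the assumed gradient, equal thirds, offer-weighted pooling, the offer frequencies in Section 5.7 and the plan's ICC of 0.5.

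A reader might infer that the primary comparison is biased or the trial underpowered for it. The documents do not support that. The randomised contrast remains a valid comparison of the two strategies as delivered, and the stated sample size is reproduced for the difference it was built to detect. This should be corrected, but it leaves the primary outcome and arm contrast as they are.

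**What to change.** 1. **Reword Section 3.1.** Describe the arm comparison as a comparison of two testing strategies. State the case-rate hypothesis separately, as a secondary, associational question.
2. **Add one secondary analysis to Section 7.10.** Pre-specify an offer-level GEE, clustered by facility, relating acceptance to county new cases per 100,000 in the past 7 days (the case indicator in Section 5.7). Compute it the same way in both arms for each four-week block. Adjust for arm, and also report the estimate within the static arm, where offer frequency is fixed. Label it non-randomised.

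Using the case indicator fixes one exposure and matches the hypothesis; the Table 1 level is the highest of three indicators. Keeping it continuous means the analysis still works if Section 5.7's fallback to trial-wide incidence tertiles is triggered, when the Table 1 high category would be nearly empty.

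The cost is SAP wording and modest analysis work. Offer dates and facility zip code are already collected (Section 7.7), so each offer can be linked to a county and block. The indicator must also be computed for any county with only a static facility. That can arise because splitting pairs is not stated and, under Section 5.3, "The governing body can request to opt out of the study". The main drawback is imprecision, as step 5 shows, so the result should be read as an estimate with its interval and not as a powered test.

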5.6 Static Testing Frequency

In discussion with the US Renal Care medical officers regarding feasibility of integrating universal testing into routine clinical care, and given that test acceptability is our chief outcome of interest, we will offer patients dialyzing in the facilities randomized to the static arm rtPCR testing once every two weeks.

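### The case-rate hypothesis in 3.1 is to be tested by the arm contrast, but the model in 7.10 names no county transmission term and the arms should face similar county rates, so a dedicated secondary analysis is needed

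*Combined protocol and SAP*

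**What the plan says.** Section 3.1: "We hypothesize that the community COVID-19 case rate will be associated with test acceptability". It goes on to say that the two offering schedules will test this, with the outcome "Proportion of offered tests accepted: # of times individuals respond yes / total # of times individuals are asked to perform the test". Sections 5.10 and 7.10 define the outcome in the same pooled way. The Protocol Overview gives the purpose as "to test the patient level acceptability of two strategies for offering test-based screening at the dialysis facility".

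On offers, section 5.6 states: "we will offer patients dialyzing in the facilities randomized to the static arm rtPCR testing once every two weeks". In section 5.7, dynamic facilities with high, medium and low evidence of community "transmission will be assigned to once weekly, once every two weeks, and once every four weeks testing respectively", reassigned every four weeks. Two rules govern the level: "If indicators suggest different transmission levels, the highest level is selected"; and, when 95% of facilities miss the high criteria, "facilities will be assigned to testing frequency strategies using trial-wide tertiles of current COVID-19 incidence".

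Sections 5.2 and 7.3 sample two facilities per county. Section 5.9 supplies county transmission data to patients and staff at dynamic units only. Section 7.10 specifies a log-binomial GEE with intervention arm as the only named predictor. It names no county level, calendar block or working correlation.

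**The concern.** A hypothesis about case rate needs a comparison between places or periods with different case rates. The arm contrast is not that comparison, because sampling within counties should give both arms much the same rates. Case rate enters the contrast only because a dynamic facility makes 4, 2 or 1 offers per patient per four weeks and a static one makes 2 throughout. The dynamic proportion is therefore weighted towards high-transmission places and periods. That weighting is mixed with any real effect of offer frequency and with the effect of county information.

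Two misreadings are at stake. A null arm difference could be taken to mean that case rate does not matter. A positive one could be taken as confirming the hypothesis, or as an effect of testing frequency as such.

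**Working it through.** **The plan's own figure.** Section 5.5 gives 0.40 v 0.65, alpha 0.05 (taken as two-sided), 80% power, ICC 0.5 and 40 patients per facility. With unpooled variance, n = (1.960 + 0.842)² × (0.40×0.60 + 0.65×0.35) / 0.25² = 58.7 per arm. The inflation factor is 1 + 39×0.5 = 20.5, giving 1,203.5 patients, or 30.1 facilities, rounded up to 31. Then 31 × 40 × 2 = 2,480, as stated.

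**Shift from offer counts alone.** Offers per four weeks are 2/2/2 (static) and 4/2/1 (dynamic) at high/moderate/low. The documents give neither acceptance by level nor the mix of levels, so both are assumed. Acceptance is set equal in the two arms at each level (no frequency effect):

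shift = Σ(mix × offers × acceptance) / Σ(mix × offers) − Σ(mix × acceptance)

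Equal thirds with 60/45/30%: (240 + 90 + 30)/7 − 45 = +6.4 points. Equal thirds is what the tertile fallback would give. A 40/40/20 mix follows from the Table 1 wastewater cut-points if percentiles are uniform. An 80/15/5 mix lies in the direction the highest-indicator rule pushes.

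**Dependence on the working correlation.** Under an exchangeable facility correlation ρ, a facility with n offers gets weight n/(1 + (n−1)ρ). Over three blocks n runs from 40×3 = 120 to 40×12 = 480. At ρ = 0.5 the weights are 120/60.5 = 1.98 and 480/240.5 = 2.00. Facilities then count almost equally, and only weighting within a facility over time remains.

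Shift in points for the 30-point gap:

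| Mix (high/moderate/low) | Independence, 4:2:1 | Exchangeable 0.5, levels redrawn each block | Exchangeable 0.5, county keeps one level | Independence, 4:2:2 |
|---|---|---|---|---|
| Equal thirds | +6.4 | +4.3 | about 0 | +3.75 |
| 40/40/20 | +5.1 | +3.5 | about 0 | +3.4 |
| 80/15/5 | +2.1 | +1.7 | about 0 | +1.7 |

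The last column applies if low spread receives two-weekly offers, as the Protocol Overview says. A 10-point gap gives one third of each entry. The shift is zero if acceptance is flat or all facilities share one level, and it reverses if acceptance falls as transmission rises.

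**Bound.** With a share p at high and the rest at low, the excess weight on high is 4p/(1+3p) − p, largest at p = 1/3, where it equals 1/3. The shift never exceeds one third of the gap, so 25 points would need a 75-point gap.

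**What the arm test detects.** Simulation used 31 county pairs, 40 patients, three blocks, ICC 0.49–0.51, no frequency or information effect, and the pooled ratio with facility-robust errors. For a 30-point gap it rejects in 7–11% (equal thirds), 6–8% (40/40/20) and 4–5% (80/15/5). For a 10-point gap it rejects in 4–6%, and with no gap in 3–6%. The result depends on the ICC. By normal approximation with equal thirds and 1,240 per arm, gaps of 20 and 40 points give 8% and 16% at ICC 0.5, but 24% and 71% at an assumed ICC of 0.05.

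**What a level comparison in static facilities detects.** Offers stay at 2 there. In the same simulation, with equal thirds or 40/40/20 and levels moving between blocks, power is 99–100% for a 30-point gap and 52–100% for a 10-point gap. If each county keeps one level it falls to 45–51% and 10–13%. At 80/15/5 with a 10-point gap it is 33–99% (moving) or 14–19% (fixed).

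**Why neither alternative arm comparison isolates frequency.** Within one level (equal thirds) the arm difference has a standard error of 11–12 points if levels move or 15–17 if fixed, against about 9 overall. Weighting by 1/offers can hide opposing effects. From a flat 45%, suppose 4 offers lower acceptance by 6 points and 1 offer raises it by 6. Equal thirds then give (156 + 90 + 51)/7 − 45 = −2.6 pooled and 0.0 weighted.

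**The case against.** The strongest reply is that the trial compares strategies. The Protocol Overview and sections 3.1, 5.10 and 7.10 mostly describe per-offer acceptance under each whole strategy. For that estimand, offering more often when transmission is high is part of the intervention. This stands in full. A reader might infer from the shift that the primary outcome is biased; the documents do not support that.

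Second, 3.1 itself expresses its hypothesis as an arm difference, and the low rejection rates set every frequency and information effect to zero. This stands in part. The trial is powered for 40% v 65%, and a strategy effect of that size could be detected. Detecting it would still not show that case rate is associated with acceptance.

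Third, a reader might infer that the trial promises an isolated frequency effect. The support is one sentence in section 6.1.5, in the consent-waiver rationale, about finding the best testing frequency. Since static and dynamic frequency are also the arm names, that sentence can mean static v dynamic. No section promises a weekly v two-weekly v four-weekly contrast.

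Fourth, the level comparison is observational. It is weak if county levels do not move, and block terms would absorb a wave shared nationally over the synchronous three months. This stands as a limit on the remedy.

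**Conclusion.** The concern holds as a mismatch between the hypothesis in 3.1 and the analysis in 7.10. No specified analysis contains case rate or transmission level, and the arm contrast carries it only indirectly. Neither a null nor a positive arm difference should be read as evidence for or against the case-rate hypothesis, or as a pure frequency effect.

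Under the assumed 30-point gap the shift runs from about 0 to +6.4 points, depending on the level mix, the unstated working correlation and how levels vary over time. The top figure is the least secure: it needs independence weighting, and it pairs equal thirds with a gap that is less plausible under the tertile fallback, when nearly all facilities are below the high criteria. That the arm test is nearly blind to case rate is true near ICC 0.5 with all other effects absent; it is not true at every ICC.

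Two stronger readings fail. The sample size reproduces, and offer weighting cannot plausibly generate the planned 25 points. This is an inexpensive improvement to what the trial can answer, not a fault in its primary comparison.

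**What to change.** In sections 3.1, 5.10 and 7.10:

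1. State that the primary estimand is per-offer acceptance of the whole strategy, and name the GEE working correlation, since it changes the estimate.
2. Prespecify a secondary analysis of the case-rate hypothesis comparing acceptance across county transmission levels within static facilities. Classify those facilities each four-week block by the same Table 1 and highest-level rules, and by the same tertiles whenever the fallback applies. Include facility and block terms and a small-sample-corrected county-level variance. Label it observational, and weak if levels do not move within counties or move together nationally.
3. Report acceptance by arm within level as descriptive only. Add a sensitivity analysis weighting each offer by 1/(offers to that patient in that block). Present neither as an isolated frequency effect.

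The cost is some analysis work and county levels for static facilities. With two facilities sampled per county, many of these levels will already be pulled for a dynamic facility. Section 7.7 already collects offer dates and facility zip codes. The weighting costs little precision at ICC 0.5, where the within-facility share of facility-mean variance is 0.0125/0.5125 = 2.4%, but more at lower ICCs.

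Separately, the Protocol Overview and section 5.7 assign different offer frequencies to low transmission and must be reconciled.
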